10.8	DATA CLARIFICATION PROCESS	40
10.9	RECORDS RETENTION	41
11 ST	TUDY MONITORING, AUDITING, AND INSPECTING	41
11.1	PROTOCOL COMPLIANCE MONITORING	41
11.2	STUDY MONITORING PLAN	41
11.3	AUDITING AND INSPECTING	41
12 PR	RIOR AND CONCOMINANT THERAPY	42
13 ST	TUDY FINANCES	42
13.1	FUNDING SOURCE	42
13.2	CONFLICT OF INTEREST	42
13.3	STIPENDS OR PAYMENTS	42
14 PU	JBLICATION OF RESULTS	42
	THICAL CONSIDERATIONS	
15 E1	I FICAL CUNSIDERATIONS	42
16 RF	EFERENCES	43

LIST OF ABBREVIATIONS

AE Adverse Event/Adverse Experience

AIS American spinal injury association Impairment Scale

ASIA American Spinal Injury Association

BWS Body Weight Support

BWST Body Weight Support Treadmill CFR Code of Federal Regulations

CRF Case Report Form
CSF Cerebrospinal Fluid
CT Computed Tomography

DSMB Data and Safety Monitoring Board
DEXA Dual Energy X-Ray Absorptiometry
ES Epidural Electrical Stimulation

EMG Electromyography

FDA Food and Drug Administration

GCP Good Clinical Practice

HIPAA Health Insurance Portability and Accountability Act

HDL High-Density Lipoprotein

Investigational Device Exemption IDE **IPG** Implantable Pulse Generator IRB Institutional Review Board Low-Density Lipoprotein LDL Modified Ashworth Scale MAS Motor Evoked Potentials **MEP** mFRT Modified Functional Reach MRI Magnetic Resonance Imaging

MRSA Methicillin-resistant Staphylococcus aureus

PHI Protected Health Information

PI Principal Investigator

SAE Serious Adverse Event/Serious Adverse Experience

SCI Spinal Cord Injury

SCI-SET Spinal Cord Injury Spasticity Evaluation Tool

SCS Spinal Cord Stimulator 6-MWT Six Minute Walk Test

SOP Standard Operating Procedure SSEP Somatosensory Evoked Potentials

TS Transcutaneous Electrical Spinal Stimulation

TMS Transcranial Magnetic Stimulation
UADE Unanticipated Adverse Device Effect

UPIRTSO Unanticipated Problems Involving Risk to Subjects or Others

WISCI-II Walking Index for Spinal Cord Injury

X-Ray X-Radiation

STUDY SUMMARY

Title	A Pilot Study to Compare Short-Term Transcutaneous or Epidural Spinal Stimulation for Enabling Motor Function in Humans with Spinal Cord Injury							
Running Title	Service Line Comparison of Transcutaneous or Epidural Stimulation							
IRB Protocol Number	21-006340							
Phase	Pilot study							
Methodology	Prospective study							
Overall Study Duration	1-year duration							
Subject Participation Duration	Less than 6 months duration per subject							
Objectives	 a. Identify relationships between stimulation inputs delivered to lumbosacral spinal circuitry and the corresponding electrophysiological outputs, during 4 weeks of motor training with stimulation, and over 16 weeks post-stimulation to determine residual effects, in individuals with SCI. b. Assess motor, sensory, and functional outcomes during 4 weeks of motor training with stimulation, and the retained effects over 16 weeks post-stimulation, in individuals with SCI. 							
Number of Subjects	8 subjects							
Diagnosis and Main Inclusion Criteria	American Spinal Injury Association Impairment Scale A-D							
Study Device	DS8R Isolated Biphasic Constant Current Electrical Stimulator (Digitimer Ltd) Abbott percutaneous trial lead for epidural neurostimulation (Model 3086) Ripple Nomad Neurostimulator							
Duration of Exposure	All subjects will complete either 1 month of transcutaneous spinal stimulation (TS) or temporary epidural spinal stimulation (ES) enabled rehabilitation sessions. Subjects will then be followed for an additional 4 months to complete follow-up assessments.							
Reference therapy	The reference therapy is clinical rehabilitation after SCI.							
Statistical Methodology	Descriptive statistics will be used to describe stimulation-related outcomes for each intervention. Repeated measures analyses of variance will be used to detect changes in outcomes over the course of rehabilitation.							

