1.2 Investigational Device

DS8R Isolated Biphasic Constant Current Electrical Stimulator (Digitimer Ltd)

Abbott percutaneous trial lead for epidural neurostimulation (Model 3086)

Abbott clinician programmer for epidural neurostimulation (Model 3874)

Ripple Nomad Neurostimulator

The temporary percutaneous implantation of epidural stimulation electrode leads will be surgically implanted to activate lumbosacral spinal networks in four humans diagnosed with chronic, complete, or incomplete loss of motor function below the level of SCI. By delivering electrical stimulation over the spinal cord during rehabilitation we aim to compare electrophysiological activity produced by spinal sensorimotor networks in response to transcutaneous or percutaneous epidural stimulation and quantify changes in motor performance metrics over the course of 12 motor rehabilitation sessions with either transcutaneous or percutaneous epidural stimulation.

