2.1 Primary Objective

The primary outcome data collected will be used to compare spinal sensorimotor activity in muscles below the level of injury during TS or ES-enabled motor tasks in persons with chronic motor complete paralysis of the lower extremities due to traumatic SCI.

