6.6 Outcome Measures

The following outcome measures will be collected as scheduled in **Table 3** with tests occurring over an approximately one-week period of time for each time point. Photographic and video images will be recorded throughout the study, but will not be shown to anyone outside the study team without the subject's written consent.

6.6.1 Primary:

Biomechanical assessments

During a variety of tasks including supine, side-lying, reaching, standing, and stepping activities, kinematics, EMG, and foot pressure measurements may be obtained, with or without spinal stimulation, using the following metrics:

Kinematics: We will use commercially available_markers placed on the skin surface via a non-irritant adhesive to record limb movement and joint angles. Available systems we may use include video-based, inertial measurement units, electromagnetic.

Electromyography: We will collect muscle activity using skin surface electrodes placed at anatomical locations of muscle groups below the level of injury. Activity will be recorded using a 16-channel signal amplifier and data acquisition system (PowerLab, ADInstruments, Colorado). At locations where self-adhesive bipolar recording electrodes will be placed onto the skin, the area will be cleaned with alcohol to ensure secure attachment and enhance signal recordings. A subset of the following muscles or muscle groups will be tested: soleus, gastrocnemius, tibialis anterior, hamstrings, quadriceps, hip adductors, gluteus maximus, gluteus medius, abdominals, triceps, trapezius, and spinal extensors.

Foot pressure: Foot pressure will be measured with shoe-insole pressure sensors (F-SCAN, Tekscan Inc., Boston, MA).

Seated pressure: Seated pressure will be assessed via a force sensing array placed beneath the buttocks (Vista Medical BodiTrak force sensing array, Winnipeg, MB, Canada).

Over the course of rehabilitation, if the research team observes stimulation-enabled functions that could be enhanced by further optimization of stimulation parameters, biomechanical assessment equipment may be used during select rehabilitation sessions in addition to the main assessment timepoints described in **Table 3**.

Table 3: Outcom	e Measure	es								
			Stı	ıdy Tin	neline					
	Screening	Pre	Implant	Spinal Stimulation + Motor training			Explant	Post	Follow-Up	
Weeks	0	Baseline		1	2	3	4		5	8, 20
Motor Training				X	X	X	X			
Urinalysis	X									
DEXA ¹	X									

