		P	rin	nary Ou	ıtcome	es				
Kinematics ²				X			X			X
EMG ²		X		X			X		X	X
SSEPs		X							X	X
TMS MEPs		X							X	X
TMS + ES or TS2		X							X	X
TS MEPs	X								X	X
ES MEPs				X			X			
BBS, TUG, 6MWT		X							X	X
FRT/mFRT				X			X			X
ISNCSCI	X								X	X
Secondary Outcomes										
Spine CT or MRI	X			X			X			
Urodynamic Studies		X							X	
Surveys		X							X	X

^{1.} DEXA scan measured at either left or right femur, and AP spine; not to include total body scan.

DEXA=Dual Emission X-ray Absorptiometry, EMG=Electromyography, SSEPs=Somatosensory Ewoked Potentials, TMS=Transcranial Magnetic Stimulation, MEPs=Motor Evoked Potentials, ES=Epidural Stimulation, TS=Transcutaneous Stimulation, BBS=Berg Balance Score, TUG=Timed Up and Go, 6MWT=6 Minute Walk Test, mFRT=Modified Functional Reach Test, ISNCSCI=International Standards of Neurological Classification of Spinal Cord Injury

^{2.} Further optimization may occur during training weeks 1-4.

Electrophysiology tests

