To assess the functional states of the spinal circuitry, we will deliver transcutaneous spinal stimulation via pulses of 1 ms duration at intensities of up to 100 mA. Stimulation will be delivered to multiple locations of the lumbosacral region with participants in a supine position. Evoked potentials will be recorded via surface EMG electrodes placed bilaterally over the soleus, gastrocnemius, tibialis anterior, hamstrings, quadriceps, hip adductors, gluteus maximus, gluteus medius, abdominals and spinal extensors. We will record evoked potentials while relaxed using stimulus intensities from 1-100 mA at increments of 10 mA for each stimulus location. Evoked potentials for each stimulus location and intensity will be averaged and visualized in real-time to determine the optimal location for evoking threshold potentials across all recorded muscles. Stimulus intensities that are at the threshold for evoking motor potentials will be delivered: while attempting prolonged maximal contractions of all muscles; during attempts to contract the left leg; and during attempts to contract the right leg. Evoked potentials will be analyzed according to task, stimulus intensity, and stimulus location.

ES MEPs

To assess the effects of delivering ES pulses to various regions of the lumbosacral spinal cord, we will record skin surface EMG from lower extremity muscles while ES is delivered to the temporarily implanted electrodes using a subset of anode/cathode configurations. Electrode configurations will be selected in order to selectively stimulate the rostral or caudal regions of the spinal cord within the T11-L1 vertebral bodies. This region of the spinal cord innervates the left and right proximal or distal muscles of the left/right lower extremities. ES pulses will be delivered as biphasic charge-balanced rectangular pulses ranging in pulse width (0.05-1ms), amplitude (0-25.5mA), and frequency (0.5-200 Hz). Within the implanted lead, each electrode could be configured as a cathode, anode, or off, and individual electrode configurations in order to target specific rostral-caudal and medial-lateral regions of the spinal cord to generate specific motor outputs.

Overground mobility

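### TS-evoked and ES-evoked potentials share no scheduled time point in Table 3, so that contrast is confounded with time and training stage

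*Combined protocol and SAP*

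**What the plan says.** Objective (a) in the Study Summary is to "Identify relationships between stimulation inputs delivered to lumbosacral spinal circuitry and the corresponding electrophysiological outputs, during 4 weeks of motor training with stimulation", and then over 16 weeks afterwards. Section 1.2 states the aim to "compare electrophysiological activity produced by spinal sensorimotor networks in response to transcutaneous or percutaneous epidural stimulation". The primary objective in section 2.1 is worded differently: to "compare spinal sensorimotor activity in muscles below the level of injury during TS or ES-enabled motor tasks".

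The relevant Table 3 rows (section 6.6) are:

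- TS MEPs: screening (week 0), Post (week 5), Follow-Up (weeks 8 and 20).
- ES MEPs: weeks 1 and 4.
- EMG: baseline, weeks 1 and 4, Post, Follow-Up.
- TMS paired with ES or TS: baseline, Post, Follow-Up.

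Footnote 2, "Further optimization may occur during training weeks 1-4", is attached to kinematics, EMG and the paired-TMS row. It is not attached to TS MEPs.

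Section 6.6.1 specifies TS MEPs closely: supine, several sites, stepped intensities, a relaxed condition and three attempted-contraction conditions. It adds that "Evoked potentials will be analyzed according to task, stimulus intensity, and stimulus location". For ES MEPs it gives parameter ranges and electrode configurations, but no posture or task. Section 1.5 says the ES electrodes are removed after the month of rehabilitation.

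**The concern.** If each kind of evoked response is recorded only when the other is not, a TS-ES difference in latency, recruitment or change over time could come from the stimulation method, from the stage of training, or from stimulation having stopped. ES responses are taken while training is under way. TS responses are taken before training and again after it has ended.

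The protocol has met this problem before. Section 1.3 reports a shorter latency with ES than with TS in two subjects whose TS recordings preceded implantation, and calls for a more structured design to settle the difference. Table 3 keeps the timing asymmetry. It also leaves objective (a) without a scheduled TS MEP in the weeks that the objective names.

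**Working it through.** The plan gives no figure to reproduce on this point. The check is one of schedule and estimability.

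**1. Is the table read correctly?** The columns were recovered from a PDF, so two cross-checks matter. The TS MEPs row has the same pattern as the ISNCSCI row, and section 4.3 places the AIS examination at screening. ES MEPs are possible only between implant and explant, which agrees with weeks 1 and 4.

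**2. Overlap.**

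- TS MEPs {0, 5, 8, 20} and ES MEPs {1, 4}: no common time.
- TS MEPs {0, 5, 8, 20} and training weeks {1, 2, 3, 4}: no common time.

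**3. Estimability.** Section 8.2 assesses the ES effect by comparing models with and without treatment indicators. Take the two MEP rows with one modality term and a categorical time effect:

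- Columns: 1 modality + 6 times (0, 1, 4, 5, 8, 20) = 7.
- Observed cells: 4 TS + 2 ES = 6, so the rank is at most 6. The computed rank is 6 of 7.
- The modality column equals the week-1 indicator plus the week-4 indicator, so modality and time are aliased exactly.
- With TS MEPs added at weeks 1 and 4 there are 6 TS + 2 ES = 8 cells. The rank is 7 of 7 and modality is estimable.

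Dropping time, or forcing a smooth shape on it, gives an estimate only by assuming away or modelling the training and decay effects that objective (a) is meant to describe.

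**4. Size of the offset.** By the table's week labels, screening to week 1 is 1 − 0 = 1 week, and week 4 to Post is 5 − 4 = 1 week.

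In sessions, at 3 per week for 4 weeks (sections 6.2 and 6.4), the target is 3 × 4 = 12:

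| Test | Sessions done at first test | Sessions done at later test | Sessions between |
|---|---|---|---|
| TS MEPs (screening, week 5) | 0 | 12 | 12 |
| ES MEPs (weeks 1, 4) | 0 to 3 | 9 to 12 | 9 − 3 = 6 to 12 − 0 = 12 |

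If the training effect were linear in sessions, which is an assumption, the same true effect would appear in ES at between 6/12 = 50% and 12/12 = 100% of its size in TS. This is only an illustration. The plan does not fix where in weeks 1 and 4 the recording falls, and Table 1 gives 12 sessions as a minimum.

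**5. Does another test fill the gap?** The paired-TMS procedure in section 6.6.1 also steps TS or ES amplitude to find a reflex threshold. Its scheduled times are baseline (before implant), and Post and Follow-Up (after explant), when ES pulses cannot be delivered. Weeks 1 to 4 are open to it only through the optional footnote.

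**The case against.** A reader might infer that the whole electrophysiological comparison between arms is confounded with time. The documents do not support that.

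- **Task EMG.** It is marked at weeks 1 and 4 in both arms and may be recorded with stimulation. The section 2.1 objective concerns activity during stimulation-enabled tasks, so it has common time points.
- **TS-evoked responses.** The TS MEPs row is not limited to one arm. If ES subjects also receive the test, TS-evoked responses can be compared between arms at screening and weeks 5, 8 and 20.
- **Objective (a).** In full it covers "corresponding electrophysiological outputs, during 4 weeks of motor training with stimulation, and over 16 weeks post-stimulation to determine residual effects". It names no between-arm contrast, and the later TS MEPs serve its residual-effects part. The TS-ES contrast comes from section 1.2.
- **Other stepped tests.** TS MEPs are not the only one. The paired-TMS procedure is another, although its schedule does not help here.

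It is also fair to say that matching the weeks would not make a difference attributable to the method. Under section 5.2 subjects enter an arm by availability or their own choice, four per arm. TS intensities run to 100 mA at the skin and ES amplitudes to 25.5 mA at the epidural surface, so raw thresholds are not on one scale. Section 3.2 declines to designate formal endpoints. The unset posture and task for ES MEPs is a specification gap and not time confounding.

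All of this stands and limits the point. It does not supply a common time for the TS-evoked versus ES-evoked contrast, or a scheduled TS MEP during training.

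**Conclusion.** The point holds for one contrast. TS-evoked and ES-evoked MEPs have no scheduled time in common, TS MEPs are never scheduled in the four training weeks, and so modality is aliased with time. The displacement is about one week on each side of training. That rests on the week labels in Table 3. It could be longer before training, because baseline testing and implantation lie between screening and week 1.

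The 50% to 100% range should not be read as an estimated bias. It depends on linearity and includes no distortion at its upper end.

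This is a moderate weakness in a descriptive pilot, and a cheap one to remove. Correcting it takes away one source of confounding and leaves those from non-random allocation with four subjects per arm.

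**What to change.** 1. In Table 3, add TS MEPs at weeks 1 and 4 for the TS arm. A reduced set at the already identified optimal site is enough.
2. In both arms, record at the start of the first training session and the end of the last. Sections 6.2 and 6.4 count any stimulation-enabled visit as a session, so the recordings belong inside existing visits.
3. Run ES MEPs in the supine relaxed and attempted-contraction conditions already written for TS MEPs.
4. State in section 8.2 that the TS-versus-ES evoked-response comparison uses weeks 1 and 4, and that weeks 5, 8 and 20 serve residual effects.
5. Compare latency, recruitment normalised to each subject's own threshold, and within-subject change. Do not compare raw thresholds in mA.
6. Reconcile the paired-TMS row with the implant and explant timing, and state whether the TS MEPs row applies to both arms.
7. Report the comparison as descriptive.

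Cost: 2 recordings × 4 subjects = 8 extra recordings of a non-invasive test already in the protocol, with equipment on hand and no new visits. The downside is longer week-1 and week-4 visits and some electrode set-up, since task EMG uses only a subset of muscles.

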1 INTRODUCTION

This document describes the protocol of a pilot stage clinical trial intended to study 8 humans diagnosed with chronic, incomplete, or complete loss of motor function below the level of traumatic spinal cord injury (SCI). The purpose of this trial is to improve the scientific understanding of how two electrical stimulation techniques, one which delivers electricity to the skin surface over the spine (transcutaneous spinal stimulation (TS)) and another which implants temporary percutaneous electrodes into the epidural space of the spinal cord (epidural spinal stimulation (ES)), facilitate spinal circuitry to enable function for individuals with SCI representing all levels of severity. Furthermore, we hope to determine responders versus non responders to spinal stimulation task-specific motor training following a condensed rehabilitation program as well as identify retained effects following 4 months of no intervention. Over the past decade, clinical investigations using either TS or ES have reported positive outcomes, such as regained control of leg movement (Gerasimenko, Lu, et al. 2015; P. S. H. PhD et al. 2011; Angeli et al. 2014; P. J. G. PhD et al. 2017; Gad et al. 2017) and cardiovascular improvements (Phillips et al. 2018; Harkema, Ditterline, et al. 2018; West et al. 2018). Independent investigations of either TS or ES have yielded some knowledge of the interactions between the electric field and spinal cord networks (Minassian, Persy, Rattay, Pinter, et al. 2007; Minassian, Persy, Rattay, Dimitrijevic, et al. 2007; Danner et al. 2016; Hofstoetter et al. 2018; Sayenko, Atkinson, Floyd, et al. 2015; Sayenko et al. 2014; Sayenko, Atkinson, Dy, et al. 2015; Rattay et al. 2000; Danner et al. 2013; Capogrosso et al. 2013).

To summarize, the paradigms used to characterize basic electrophysiological responses to stimulation in prior studies differed significantly from those used to facilitate functional movements in participants with lower extremity paralysis, specifically stimulation intensity and frequency. Therefore, there is a gap in knowledge of the electrophysiological and biomechanical outcomes produced by function-enabling TS and/or ES waveforms. Further, there is a lack of knowledge of the functional impact of brief rehabilitation with spinal stimulation in humans with SCI impairments. Finally, the extent to which stimulation-related changes are retained following the intervention is unknown. This protocol describes the experiments we will carry out to address this gap in knowledge of the interactions of either TS or ES over the course of brief rehabilitation periods. This clinical trial will be carried out in accordance with the procedures described in this protocol, applicable United States government regulations, and Mayo Clinic policies and procedures. All study procedures will be performed at Mayo Clinic's campus in Rochester, Minnesota.

1.1 Background

Spinal cord injury

Severe SCI results in permanent loss of motor, sensory, and autonomic functions below the level of injury, leading to in catastrophic, lifelong changes in quality of life for SCI survivors. In the United States of America, nearly 300,000 people are living with neurological deficits due to SCI (National Spinal Cord Injury Statistical Center 2017). The effects of SCI are defined relative to physical and functional characteristics. It is well accepted that trauma to the spinal cord leads to functional disconnection of ascending and descending neural pathways between brain circuitry, spinal cord networks, and peripheral end organs, impairing

bodily functions innervated by spinal cord networks located below the lesion (Kandel 2013). A systematic review of studies that directly surveyed people with SCI found that the major priorities of functional recovery were: motor function (arm/hand for tetraplegia and mobility for paraplegia), bowel, bladder and sexual function, as well as a desire to improve psychosocial health (Simpson et al. 2012).

Spinal electrical stimulation to enable functions after SCI

Significant progress has been made in the field of spinal electrical stimulation to enable motor functions previously thought to be permanently lost after SCI. Specifically, Harkema and colleagues reported that, after months of rehabilitation with ES, volitional control of joint-specific muscles and independent standing were achieved by four humans with motor complete paraplegia (Harkema et al. 2011; Angeli et al. 2014). Recently, we reported that ES enabled control of stepping leg movements, which over the course of rehabilitation, translated to independent standing and stepping (Grahn et al. 2017; Gill et al. 2018). In addition to reports of ES enabling lower extremity motor functions, improvements in upper extremity (Lu et al. 2016), cardiovascular (Harkema et al. 2018; West et al. 2018; Harkema, Wang, et al. 2018; Aslan et al. 2018), and urologic functions (Herrity et al. 2018) have been reported.

In parallel investigations, electrical stimulation applied to the skin surface over the spine (i.e., TS) has emerged from prior use as a neurophysiological tool to interrogate spinal circuitry, (Danner, 2016; Sayenko, 2015; Sayenko, 2015; Krenn, 2017; Andrews, 2015; Roy, 2014) to a non-invasive approach to facilitate spinal circuitry and generate coordinated motor activity below the level of SCI (Inanici et al. 2018; Gad et al. 2018; Gerasimenko, Lu, et al. 2015; Gad et al. 2017). Similar to ES, TS has recently been shown to improve cardiovascular (Phillips et al. 2018) and urologic functions (Gad et al. 2018).

Pathophysiology relevant to potential study treatment action

Evidence from human cadavers suggests that even in cases diagnosed as complete loss of function below the level of SCI, as defined by the American Spinal Injury Association Impairment Scale-A (AIS-A), a portion of neural tissue commonly remains intact across the injury site (Kakulas 1984). These intact tissues may transmit non-specific supraspinal signals to sublesional spinal circuitry (Dimitrijevic et al. 1983). The unique electrophysiological characteristics associated with this injury profile have led to an injury description known as "discomplete SCI" (Dimitrijevic et al. 1983; McKay et al. 2004; Sherwood et al. 1992). The mechanisms by which TS and ES enable volitional control are thought to involve facilitation of sublesional spinal networks to that a "functional" state of excitability in order to properly receive signals transmitted across the discomplete SCI and to produce functional outputs (Grahn et al. 2017; Gill et al. 2018; Taccola et al. 2018).

TS and ES interactions with spinal circuitry have been preliminarily investigated using computational models (Capogrosso et al. 2013; Danner et al. 2015; Rattay et al. 2000; Danner et al. 2011) and basic properties of the evoked spinal motor potentials have been described (Sayenko et al. 2015; Sayenko et al. 2014; Sayenko et al. 2015; Danner et al. 2016; Hofstoetter et al. 2018). However, the stimulation paradigms used in prior studies were focused on eliciting motor potentials via single stimulus pulses in order to establish a basic

understanding of the evoked response properties during electrical facilitation of spinal circuitry (i.e., the intent was not focused on enabling functional activities that had been lost in subjects with SCI).

Description of the population to be studied

This study will include adult humans that sustained a traumatic SCI at least one year before trial enrollment. To qualify for this study, SCI severity must be previously diagnosed with an AIS classified injury. One participant will be enrolled from each AIS classification (A, B, C, and D) for each intervention. All injuries must be located at or above the tenth thoracic vertebrae. Detailed inclusion and exclusion criteria are provided within the appropriate section of this protocol.

